7.5 Removal of Subjects

Subjects may be taken off the study treatment and/or removed from the study at any time at their own request. Subjects may also be withdrawn at the discretion of the investigator for safety, behavioral (e.g., subject not compliant with study treatment for more than two continuous weeks) or administrative reasons.

The reason(s) for discontinuation will be documented on the End of Study eCRF.

Reasons for withdrawal may include:

- Patient voluntarily withdraws from treatment (follow-up permitted);
- Patient withdraws consent (termination of treatment and follow-up);
- Patient is unable to comply with protocol requirements;
- Patient experiences adverse reaction that makes continuation in the protocol unsafe;
- Investigator determines continuation on the study would not be in the patient's best interest;
- Patient becomes pregnant during treatment period;
- Patient is lost to follow-up.

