7.2.4 Visit #4. Bronchoscopy #2 / Treatment Session #2

Subjects are scheduled for follow-up 3-6 weeks following Bronchoscopy #1. Pre-operative procedures (e.g. CT Scan, physical exam, CBC) are completed in accordance with the Schedule of Events table prior to the bronchoscopy. Any observed adverse events are reported accordingly. If the subject has experienced any complications that preclude continued participation in the study, then additional treatment is halted.

Upon successful completion of the pre-operative procedures, the subject undergoes a bronchoscopy procedure in accordance with standard institutional protocol. Anesthesia is administered. The airways are visualized, and BAL completed. The RheOx Bronchial Rheoplasty is administered to the target sites in the left side lung in accordance with the instructions for use. The clinical investigator ensures FiO₂ does not exceed 40% during energy delivery. Prior to the initiation of energy delivery and during at least one energy delivery a 6 second 3 lead EKG strip is recorded. An EKG rhythm strip from anesthesia monitoring is adequate.

The subject is recovered in accordance with standard institutional procedures and observed overnight at the discretion of the study investigator. The subject is then discharged at the investigator's discretion. Any observed adverse events are reported accordingly.

Note: Bronchoscopy #2 may be delayed or halted at the investigator's discretion if the patient has an active respiratory infection (e.g., common cold, pneumonia, MAI), COPD exacerbation since treatment session #1 or any other significant clinical symptom that may compromise the procedure.

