Additional Notes on Schedule of Events:

Note: If Bronchoscopy #2 cannot be completed the subject should continue follow-up at 3 months, 6 months, 12 months and annually through 5 years following Bronchoscopy #1 (i.e., last treatment session).

Note: If the subject experiences a COPD exacerbation or other change in functional status within 6 weeks of any scheduled follow-up visit, the investigator should consider rescheduling study follow-up visits based on his or her best medical judgement to allow for an accurate assessment of the patient's stable condition once the subjects symptoms have returned to normal. It is recommended that subjects return to clinical baseline for a minimum of two-weeks prior to undergoing study specific follow-up testing.

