6 LIST OF TABLES

No.	Title	Population
14.1.1	Patient Disposition	All Patients
14.1.2	Patient Follow-up Status	All patients
14.1.3	Patient Enrollment and Disposition by Site	All patients
14.1.4	Protocol Deviations	Evaluable
14.1.5	Demographic and Baseline Characteristics	Evaluable
14.2.1	Procedure Results	Evaluable
14.2.2	Concomitant Medications through 12 Months	Evaluable
14.2.3	Concomitant Medications Post 12 Months	Evaluable
14.2.4	Quality of Life Outcomes through 12 Months	Evaluable
14.2.5	Quality of Life Outcomes Post 12 Months	Evaluable
14.2.6	HRCT Scan Quantitative Analysis	Evaluable
14.2.7	Pulmonary Function Testing through 12 Months	Evaluable
14.2.8	Pulmonary Function Testing Post 12 Months	Evaluable
14.2.9	Responder Analyses	Evaluable
14.3.1	Serious Adverse Events of Interest and Hospitalizations	Evaluable
14.3.2	High Level Summary of Non-Serious Adverse Events	Evaluable
14.3.3	High Level Summary of Serious Adverse Events	Evaluable
14.3.4	Non-Serious Adverse Event Summary through 12 Months	Evaluable

CONFIDENTIAL:

This document and its contents are the property of Gala Therapeutics, Inc. Any use, reproduction or distribution without the written permission of Gala Therapeutics, Inc. is prohibited.

	TYPE: Clinical Trial Document	Document No:	CLN-0000X
	TITLE: CS003 Statistical Analysis Plan	Revision:	A
		Release Date:	
		DCN	Page 14 of 44

No.	Title	Population
14.3.5	Non-Serious Adverse Event Summary Post 12 Months	Evaluable
14.3.6	Serious Adverse Event Summary through 12 Months	Evaluable
14.3.7	Serious Adverse Event Summary Post 12 Months	Evaluable
14.3.8	COPD Exacerbation Rates	Evaluable

CONFIDENTIAL:

This document and its contents are the property of Gala Therapeutics, Inc. Any use, reproduction or distribution without the written permission of Gala Therapeutics, Inc. is prohibited

	TYPE: Clinical Trial Document	Document No:	CLN-0000X
	TITLE: CS003 Statistical Analysis Plan	Revision:	A
		Release Date:	
		DCN	Page 15 of 44

Table #14.1.1 Patient Disposition

All Patients

Patient Status

Number of patients consented	xx
Excluded	xx/xx (xx.x%)
In Screening	xx
Enrolled (Treated)	xx/xx (xx.x%)
In Follow-up	xx/xx (xx.x%)
Completed Study	xx
Exited Study	xx
Withdrawn by Investigator	xx
Subject Withdrew Consent	xx
Death	xx
AE / SAE (other than death)	xx
Lost to Follow-up	xx
Other	xx

CONFIDENTIAL:

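### Protocol 7.5 does not separate stopping RheOx treatment from leaving the study, so investigator withdrawals can leave the 12-month safety incidence unresolved and biased downward

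*Protocol*

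**What the plan says.** Protocol 7.5 first distinguishes coming off treatment from leaving the study, but only for the subject's own request. It then adds: "Subjects may also be withdrawn at the discretion of the investigator for safety, behavioral" or administrative grounds, without that distinction. The listed reasons include "Patient experiences adverse reaction that makes continuation in the protocol unsafe" and "Patient is unable to comply with protocol requirements". Two reasons state what happens to follow-up. One is "Patient voluntarily withdraws from treatment (follow-up permitted"; the other is withdrawal of consent, which ends both treatment and follow-up. The remaining reasons are silent. One form serves all of them: "The reason(s) for discontinuation will be documented on the End of Study eCRF".

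Two other places bear on the same subjects. Section 7.2.4 says "If the subject has experienced any complications that preclude continued participation in the study, then additional treatment is halted", so its condition concerns study participation and its consequence concerns treatment. The additional notes to Table 7.1 say "If Bronchoscopy #2 cannot be completed the subject should continue follow-up at 3 months, 6 months, 12 months and annually through 5 years", counted from the first bronchoscopy.

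In the SAP, the rows after the Exited Study line of Table 14.1.1 include withdrawal by the investigator and "AE / SAE (other than death". Section 4.8.1 reports the primary outcome as the count and percentage of patients with each event of interest, and with any of them, through the 12-month visit. Section 5.2 uses all available data and rules out imputation and any other assessment of missing data.

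**The concern.** RheOx is given in two sessions about four weeks apart (protocol synopsis). After Visit 4 no study treatment is left to stop, so from then on withdrawal by the investigator can only end observation. The example of non-compliance in 7.5, a lapse from study treatment of over two weeks, suits a continuous therapy and has no meaning for two single procedures.

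The primary outcome counts events over the whole 12 months, including death, hospitalised exacerbation, respiratory failure and arrhythmia. Several complications foreseen in protocol 10.2 could prompt withdrawal without being endpoint components: airway stenosis, lung abscess and significant pulmonary bleeding. If a subject leaves after one of these, a later death or admission may not reach the database, yet the subject can still be counted as event-free. Exit for an adverse reaction is plausibly related to later risk, so the reported incidence would tend to be too low. SGRQ, CAT and hospitalisation data would be lost in the same subjects.

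**Working it through.** The plan has no calculated figure to reproduce. SAP 4.1 states that no formal sample size calculation was done, and neither document gives an event rate or a dropout rate. The check is therefore a comparison of the texts, followed by bounds.

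**Which text governs follow-up**
- Stopped after the first session: the Table 7.1 note keeps the subject in follow-up. Section 7.5 is silent, and the note does not refer to it. A site could apply either.
- Withdrawn by the investigator after both sessions: the note does not apply, and 7.5 is again silent. The only record is the End of Study form, and the SAP provides exit rows.
- Subject withdraws consent: 7.5 ends follow-up. This case is clear.

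**Bounds on the primary incidence**

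Inputs: N = 30, the maximum in protocol 8.2. Assumed: x subjects with an observed event and k subjects removed event-free before 12 months.

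The range is x/N to (x + k)/N, and each removed subject adds 1/30 = 3.3 points.
- x = 3, k = 1: 3/30 to 4/30 = 10.0% to 13.3%
- x = 3, k = 3: 3/30 to 6/30 = 10.0% to 20.0%
- x = 3, k = 5: 3/30 to 8/30 = 10.0% to 26.7%
- x = 0, k = 3: 0/30 to 3/30 = 0% to 10.0%

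The exact 95% interval is 2.1% to 26.5% for 3/30 and 7.7% to 38.6% for 6/30. If the removed subjects also leave the denominator, x = 3 and k = 3 gives 3/27 = 11.1%, still near the lower bound.

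**Expected shortfall under assumed risks**

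Assume a 12-month risk p in subjects who stay, RR × p in those removed, risk spread evenly over the year, removal at month m, no capture afterwards, and a denominator of 30. The shortfall is k × RR × p × (1 − m/12) / 30. For k = 3:
- m = 1, p = 10%, RR = 1: 3 × 0.10 × (11/12) / 30 = 0.92 points
- m = 1, p = 20%, RR = 2: 3 × 0.40 × (11/12) / 30 = 3.7 points
- m = 1, p = 30%, RR = 3: 3 × 0.90 × (11/12) / 30 = 8.25 points
- m = 6, same extremes: 0.5 to 4.5 points

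**Effect of the denominator**

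Assume risks of 15% in those who stay and 40% in those removed, with removal so early that all their events are missed.
- k = 2: true (28 × 0.15 + 2 × 0.40)/30 = 16.7%. Reported 4.2/30 = 14.0% or 4.2/28 = 15.0%, which is 2.7 or 1.7 points low.
- k = 4: true (26 × 0.15 + 4 × 0.40)/30 = 18.3%. Reported 3.9/30 = 13.0% or 3.9/26 = 15.0%, which is 5.3 or 3.3 points low.

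SAP 4.8.1 does not define the denominator, and Table 14.3.1 shows a separate N for each period, so either could be used.

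**The case against.** The other side has four good arguments.

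- **The text is permissive.** Section 7.5 says what may happen, and the only reason that expressly ends follow-up is withdrawal of consent. A reader might infer that 7.5 requires follow-up to stop after an adverse reaction or non-compliance. It does not; it leaves the matter unstated. The notes to Table 7.1 also exclude lapses in the daily EXACT-PRO diary as a ground for removal.
- **Part of the gap is already closed.** The Table 7.1 note covers subjects whose treatment is stopped between sessions, and the stated consequence in 7.2.4 is only that treatment halts. This stands for those subjects, although the sections still need to be reconciled. It does not reach subjects who have had both sessions.
- **Later events are not certain to be lost.** A reader might infer that events after exit would never be seen. Protocol 10.1.2 requires investigators to report serious events when they learn of them and sets no cut-off at exit, and 10.1.3 calls for reports on the later course of an event. Without visits or calls, though, an investigator is less likely to learn of a new event. Capture is weakened, not abolished.
- **The study is small and descriptive.** No safety test or success threshold depends on the result (SAP 4.8). The exact interval for 3/30 is wider than most of the shortfalls above. SAP 4.3 lists the reason and last date of participation for early withdrawals, so a careful reader could construct bounds. This limits the consequence, but safety is the primary objective and sampling intervals do not describe a one-sided loss of information.

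Two further limits apply. A subject removed because of a qualifying event already counts in the composite. The link between removal and later risk is a reasonable inference for adverse reactions but weaker for non-compliance, and the documents give no data on either.

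**Conclusion.** The point holds as a gap in the wording with a possible downward effect on the primary safety incidence. For investigator withdrawals, section 7.5 does not separate the end of treatment from the end of participation. The Table 7.1 note protects only subjects without a second bronchoscopy, and the planned analysis does nothing to show or repair the loss.

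The firm figure is up to 3.3 points unresolved for each subject removed event-free before 12 months, taking N = 30. The range of 10.0% to 20.0% assumes 3 observed events and 3 such removals. The documents do not support any single estimate of bias: the number of removals, their timing and their later risk are all unknown, and the answer also depends on the denominator. The amendment is worth making because it is cheap and concerns the primary outcome.

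**What to change.** **Protocol**
- Reconcile 7.2.4, the Table 7.1 note and 7.5 so that stopping treatment and leaving the study are separate decisions, recorded separately.
- State that a subject whose treatment is stopped, or whom the investigator withdraws from study procedures, stays in safety follow-up through 12 months unless consent is withdrawn. This covers adverse events, hospitalisation and vital status, by visit, telephone or records.
- Delete the two-week non-compliance example.
- Leave to the investigator whether treatment stops and which procedures a given subject should undergo.

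**SAP**
- Keep the exit rows of Table 14.1.1, since section 4.3 requires exits and their reasons to be reported. Add a line for treatment stopped with follow-up continuing.
- Beside the primary percentage, report the range x/N to (x + k)/N, where k is the number of subjects who exit event-free before 12 months, and state N.

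If follow-up is complete, k from this cause is 0 and the range closes to one figure. With 3 events in total, that is 3/30 = 10.0% (exact 95% interval 2.1% to 26.5%).

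The cost is an amendment to the protocol and consent wording, one table line, one sensitivity row, and a few extra follow-up contacts. No new procedure is needed.

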7.6 Early Termination or Suspension of Study

7.6.1 Study Stopping Rules

Study enrollment and further treatment of any subject will be halted if any of the following serious adverse events are observed in a given subject;

- Death associated with the study investigational therapy or procedure
- Three or more subjects with a pneumothorax within 2 days of either Gala Treatment procedure
- Device related arrhythmias requiring cardioversion or sustained VT regardless of intervention
- Acute pulmonary hemorrhage requiring surgical intervention or embolization
- Unanticipated adverse device effect

The study may not resume enrollment until the study medical monitor, the sponsor and principal investigator have reviewed the observation and events

surrounding the observation to determine if the study should be halted or may continue.

7.6.2 Interim Safety Analysis

In addition to the study stopping rules, an interim safety analysis will be conducted after 5 subjects complete the second treatment (Visit 4) to ensure it is safe to continue study treatments. Enrollments and planned study visits/treatments should continue per the study protocol while the interim analysis is being conducted. The interim analysis will consist of a review of all AE and SAE data collected in the study at that point including an assessment of device and procedure relatedness. The data will be reviewed by the study medical monitor and a subcommittee of three Gala Therapeutics Scientific Advisory Board members, composed of experts in chronic bronchitis and interventional bronchoscopy procedures to ensure it is safe to continue the study. Patient demographics and procedural characteristics will also be included in the review. The review should confirm that the safety profile of the study is consistent with expectations set forth at the start of the study.

Recommendations may include:

1. Continue the study without modification
2. Continue the study with modification or
3. Terminate the study

8.0 STATISTICAL CONSIDERATIONS

8.1 Study Design

This is a prospective, single arm feasibility study of RheOx in patients with chronic bronchitis. Neither subjects nor investigators will be blinded.

8.2 Sample Size

As this is an early feasibility study, up to 30 subjects will be enrolled and treated with the study device to assess the effect of the investigational device in the target population.

8.3 Evaluable Cohort

All subjects who have entered the treatment room for Visit #2 will be included in the safety endpoint analysis (Safety Population). Subjects who have received at least one treatment will be included in the evaluable cohort for clinical utility.

8.4 Outcome Analysis

Descriptive statistics will be utilized to summarize and report on data for all subject and outcome variables. Categorical data (e.g., age, gender) will be reported in frequency distributions. Certain dichotomous data (e.g., subjects with Serious Adverse Events) will also be presented as rates. Continuous data (e.g., age, FEV₁) will be summarized using mean, standard deviations, medians, minimums, maximums, and interquartile ranges. Additional subgroup and other multivariable analyses may be performed including examination of the association between subject risk factors (e.g., age, gender) and trial outcomes, and the potential contributions of these factors.

9.0 DATA MANAGEMENT

9.1 Data Entry

Source documents shall be maintained by the investigational sites throughout the course of the investigation. All findings in this investigation must be documented as source data, and therefore can be verified and audited. Source documentation may be paper or electronic and is defined as the first time the data appears and may include for example; all questionnaires, phone interview notes, clinical records, hospital records, surgery reports, death/autopsy reports, and any other material that contains original information used for clinical study data collection or adverse event reporting. It should be possible to verify the inclusion and exclusion criteria for the investigation from available source data. Source documents must include the subject identification number and a date.

Data obtained from each subject during the clinical trial will be entered in the electronic data capture (EDC) database within five working days of the report date. All applicable sections of the EDC case report forms (eCRFs) must be filled out completely. The EDC system and associated data collected over the course of the study will be managed per the approved study Data Management Plan.

9.2 Subject Data Protection

Upon enrollment in the study, each subject will be assigned a unique identifier in accordance with GCP. Subject data will be recorded using the unique identifier. The subject's name or any other identifying label will not be recorded on the CRFs.

In accordance with applicable regulations (e.g., HIPAA), subjects who have provided written informed consent must also sign a subject authorization to release medical information to the study sponsor and/or their representatives and allow regulatory authorities such as FDA access to subject's medical information relevant to the study.

9.3 Data Retention

Study documentation includes all CRFs, data correction forms or queries, source documents, correspondence, monitoring logs and letters, and regulatory documents (e.g., CIP and amendments, IRB correspondence and approval, signed patient consent forms). Source documents include all recordings of observations or notations of clinical activities and all reports necessary for the evaluation and reconstruction of the clinical research study.

The study sponsor or investigator(s) must retain all study documentation pertaining to the conduct of the study in accordance with applicable regulations. These documents shall be retained during this investigation and for a period of at least two years after the later of the following two dates: the date on which the investigation is terminated or completed, or the date of the last approval of marketing application in an ICH region.

9.4 Monitoring

The Sponsor, or designee, will monitor the clinical investigation in accordance with GCP and all applicable regulations. The Monitor must ensure that the investigation is conducted in accordance with the signed Investigator Agreement, the Clinical Investigational Plan, any conditions imposed by the IRB, and applicable regulations.

Monitoring intervals will occur as described in the clinical monitoring plan. The Monitor will notify the Sponsor within 24 hours upon becoming aware of any UADE not previously reported to the Sponsor. In the event the investigator is not complying with the study requirements, it is the Sponsor's responsibility to secure compliance.

10.0 ADVERSE EVENTS

10.1 Reporting Requirements

10.1.1 Adverse Events

Adverse events will be reported on the adverse event eCRF. All adverse events will be graded according to Medical Dictionary for Regulatory Activities (MedDRA).

Adequate information related to the adverse event must be supplied to the Sponsor to determine whether the adverse event is related to use of the investigational device. The study investigator should assess to the best of their ability relatedness of each AE to the study device and study procedure(s) according to the following categories; not related, possibly related, and probably related.

AE severity is assessed by the study investigator and recorded on the AE eCRF according to the following definitions;

- Mild (Grade 1): the event causes discomfort without disruption of normal daily activities.
- Moderate (Grade 2): the event causes discomfort that affects normal daily activities.
- Severe (Grade 3): the event makes the patient unable to perform normal daily activities or significantly affects his/her clinical status.
- Life-threatening (Grade 4): the patient was at risk of death at the time of the event.
- Fatal (Grade 5): the event caused death.

AEs collected over the course of the study will be regularly monitored by the study medical monitor and/or other company representatives or consultant advisors (if deemed necessary) to ensure the ongoing safety of the study.

10.1.2 Serious Adverse Events

All serious adverse events must be reported to the Sponsor within 24 hours after the investigator first learns of the event, regardless of presumed relationship to the device or trial. In addition, the investigator and the Sponsor will comply with IRB and FDA reporting requirements, inclusive of reporting requirements defined in 21 CFR 812.150.

10.1.3 Unanticipated Adverse Device Effect

An investigator shall submit to the sponsor a report of any unanticipated adverse device effect occurring during an investigation as soon as possible, but in no event later than 10 working days after the investigator first learns of the effect.

Reports relating to the patient's subsequent medical course must be submitted to the Sponsor via the study eCRFs until the event has subsided or, in case of permanent

impairment, until the event stabilizes, and the overall clinical outcome has been ascertained. For reported deaths, the investigator should supply the Sponsor and the IRB with any additional requested information (e.g., autopsy reports and terminal medical reports).

The Sponsor is responsible for reporting all serious and unexpected adverse device effects to FDA in an expedited manner, and in accordance with all applicable federal regulations. The Sponsor will expedite the reporting in compliance with ICH GCP to all concerned investigators. The investigator will report to the IRB in accordance with institutional requirements, but no later than 7 calendar days of first knowledge.

10.2 List of foreseeable adverse events related to investigational therapy and/or study procedure:

- Sore throat (likely occurrence)
- Coughing (likely occurrence)
- Hemoptysis (likely occurrence)
- Minor complications associated with anesthesia (moderate likely occurrence) including nausea, vomiting, bruising at the site of injections, sore throat or hoarse voice, urinary retention
- Infection (moderately likely occurrence) including fever, pain or soreness
- Exacerbation (moderately likely occurrence) including shortness of breath, increased color and/or quantity of phlegm
- Bronchial perforation (low occurrence)
- Lung abscess (low occurrence)
- Gastroparesis (low occurrence)
- Pneumothorax (low occurrence) including severe chest pain, trouble breathing, death
- Airway stenosis (low occurrence) including wheezing, hoarseness, shortness of breath and/or respiratory distress
- Abnormal cardiac rhythm function (low occurrence) including arrhythmia, atrial fibrillation, ventricular fibrillation, death
- Allergic reaction (low occurrence) including abnormal breathing, difficulty swallowing, anxiety, chest pain, severe cough, lightheadedness or dizziness, sweating or fainting, swelling of the face, eyes or tongue
- Significant pulmonary bleeding (low occurrence)
- Significant complications associated with anesthesia (low occurrence) including damage to teeth, aspiration, respiratory failure, brain damage, and death
- Death (low occurrence)

Note: Likely occurrence is estimated to occur in more than 1 in 2 patients. Moderately likely occurrence is estimated to occur in 1 in 10 to 1 in 100 patients. Low occurrence is estimated to occur in less than 1 in 100 patients.

